10.1.4. Safety Endpoints

10.1.4.1. Time to Reach Complete Wound Closure

The analyses of the safety endpoint time to complete wound closure on a target wound level will compute missing values as censored at the date of the last non-missing wound closure assessment. If no wound closure assessment after baseline is available, the target wound will be censored with time 0.

For additional analyses on a subject level, if a subject has a wound which did not reach complete closure, the time will be censored at last date of wound closure assessment. If a

subject has a wound with no wound assessment available after baseline, the subject will be censored with time 0.

Note: the additional analysis on a subject level had been added per FDA recommendation.

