10.3.4. Safety Endpoints

10.3.4.1. Time to Reach Complete Wound Closure

Information about date will be transformed to time in days from randomization. Missing values will be addressed as described in Section 10.1.4.1.

For the purpose of the main analysis, time until complete wound closure (for definition see Section 6.1), will be defined as the time (in days) until complete wound closure has been achieved at a wound level. The definition of complete wound closure demands that the wound closure is to be confirmed at two consecutive study visits, 2 weeks, i.e. 14 (± 2 days), apart. A wound is only to be regarded as closed in this analysis if the wound was closed at a wound closure assessment and this was confirmed at an additional assessment within 12-16 days from the initial closure assessment. In case wound closure is not confirmed in the pre-defined time frame the wound is considered not completely closed at the first closure assessment.

Additionally, for the SoC group, a variable for time to wound closure will be calculated as above, but in the non-inferiority comparison, a 7 days non-inferiority margin will be added.

For additional analyses on a subject level, time to complete wound closure of all target wounds (last healing wound) will be computed, i.e. the time from randomization (in days) to subject's last wound closure.

For supportive analyses, the time to reach 100% wound closure will be computed on a wound level and on a subject level, where the complete wound closure is defined as 100% of wound area epithelialized and/or closed by graft without drainage or dressing requirements confirmed at two consecutive study visits, 2 weeks apart.

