11.1.5.1. Time to Reach Complete Wound Closure

For the purpose of the main analysis, time to reach complete wound closure will be compared between the NexoBrid and SoC at a wound level using a method of survival analysis with clustered data that is based on appropriate assumptions. By "clustered data", we refer to the

multiple target wounds that can occur in a patient. As stated in the protocol, a non-inferiority margin will be incorporated into the analysis that will represent a 7-day advantage to the SoC group. This will be done by adding 7 days to the wound closure times in the SoC group. After that, the proportional hazards assumption will be checked in the same way as in the analysis of the timely eschar removal endpoint. I.e. a Cox regression model will be fitted with covariates treatment, center, age, %TBSA, proportion of the FT area of a patient, number of TWs (1,2,3-4, ≥5) and a variable representing the interaction between time since randomization and treatment group. The latter coefficient will be tested to be nonzero. Additionally, a log likelihood test comparing the model fit of a model with all time by covariate interactions added with a model without these interactions will be computed. The proportionality assumption will be rejected if one of these tests yields a significant result at the 10% level. If the proportional hazards assumption is appropriate we will use a marginal Cox regression analysis with a robust sandwich estimator. If not, then we will use a parametric frailty model. Either method can be implemented in SAS (see Gharibvand and Liu, 2009 for details). The marginal Cox regression model is implemented in the PHREG procedure and the robust variance option is implemented by specifying the COVS(AGGREGATE) option. This induces the use of the robust variance method of Binder et. al. [22]. The parametric frailty model will be implemented using the following SAS-code:

```
PROC PHREG DATA=burn_data;
CLASS Subject_id treatment_group centergroup numtw;
MODEL time*status(0) = treatment_group centergroup age tbsa pctFT numtw;
RANDOM Subject_id;
HAZARDRATIO "Frailty Model" treatment_group;
RUN;
```

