where subject_ID is a unique identification number for each patient, time is the time to wound closure on a wound level. Censor is a censoring indicator, treatment_group gives the treatment group, age1-age3 are indicator variables for a subject being in age group A1 − A3 respectively (per age groups defined in Section 11.1.11), ft1is an indicator for a subject with proportion of the FT area <20% out of the total burned area (group C1, defined in Section 11.1.11), TBSA1 is an indicator for a subject with overall %TBSA in (1% to 15%), inclusive (group B1, defined in Section 11.1.11), number_tw2 is an indicator variable for the subject having 2 target wounds (patient level), number_tw3 is an indicator variable for the subject having 3-4 target wounds (patient level), number_tw4 is an indicator variable for the subject having ≥5 target wounds (patient level), US, EEU and WEU are indicator variables for the individual being in region US, EEU and WEU (patient level) and burn_data is a SAS data set containing the required information.

Kaplan-Meier curves will be presented graphically to display the distribution of time to complete wound closure under the two treatments.

If any of the baseline factors are found to be significantly different between the treatment groups (based on the analyses described in Section 11.1.1), then the factor will be included as an extra adjusting covariate in a supportive analysis of time to complete wound closure.

As an additional analysis, the time to complete wound closure will be analyzed on a subject level. Kaplan-Meier curves will be presented graphically to display the distribution of time to complete eschar removal under the two treatments on a subject level. Median time to complete eschar removal will be estimated for each treatment group with a 95% confidence interval. Furthermore, descriptive statistics for time to complete eschar removal will be presented. The treatment groups will be compared using either a Cox regression model (if the proportional hazards assumption appears to hold), or a generalized Wilcoxon-Gehan test (if the proportional hazards assumption does not hold), as described in Section 11.1.3 for the main analysis of the primary efficacy endpoint.

As supportive analyses, the time to reach 100% wound closure will be analyzed on a wound level (similar to the main analysis outlined above) and on a subject level (similar to the additional analysis outlined above).

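### The subject-level wound-closure analysis names eschar removal in its outputs and, on a natural reading, tests for no difference without the 7-day margin, so it could not show non-inferiority if the arms were similar

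*SAP*

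**What the plan says.** The main analysis of time to wound closure (SAP 11.1.5.1) is done "at a wound level using a method of survival analysis with clustered data". The margin enters there: "As stated in the protocol, a non-inferiority margin will be incorporated into the analysis that will represent a 7-day advantage to the SoC group". It is applied by lengthening every SoC closure time by 7 days before the model is fitted.

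SAP 10.3.4.1 derives the variables in this order:
- the wound-level closure time;
- a SoC version of it, built the same way, with 7 days added for the non-inferiority comparison;
- in the next paragraph, the subject-level time: "For additional analyses on a subject level, time to complete wound closure of all target wounds (last healing wound) will be computed". No shift is mentioned there.

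SAP 10.1.4.1 gives the origin of the subject-level work: "the additional analysis on a subject level had been added per FDA recommendation".

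In SAP 11.1.5.1 the lead sentence of the subject-level analysis names wound closure. The next three sentences, on Kaplan-Meier curves, medians and descriptive statistics, name eschar removal; one reads "Median time to complete eschar removal will be estimated for each treatment group with a 95% confidence interval". The comparison follows: "The treatment groups will be compared using either a Cox regression model (if the proportional hazards assumption appears to hold", with a generalized Wilcoxon-Gehan test otherwise, both by reference to SAP 11.1.3. That section tests a null of no difference. The general rule at the start of SAP 11 is two-sided at 0.05 unless stated otherwise, and nothing else is stated here. The supportive subject-level analysis of 100% closure is modelled on this one.

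**The concern.** The SAP treats wound closure as a non-inferiority question, both in the main analysis and in the power section (SAP 13.3). The child is the randomized unit, so the subject-level analysis is the one at the level of randomization. Without a margin it answers a different question. A non-significant result would say nothing about whether closure is delayed by less than 7 days. A significant delay shorter than 7 days would be reported with no reference to the margin.

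The output wording is a separate fault. The wound-level text in 11.1.5.1 asks for Kaplan-Meier curves but not medians. The only sentence in that section asking for a median with a confidence interval therefore names the wrong endpoint. SAP 6.4 requires the analysis to follow the plan and relies on double programming, so two programmers could reasonably produce different tables.

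**Working it through.** **1. The plan's own figures, with the margin built in (SAP 13.3).** D = 4(z_α + z_β)² / (ln λ)² and n = 2D / (p1 + p2), with z_α = 1.96 and z_β = 1.28.

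- MW2004-11-02 (ln λ = 0.18; p1 = 0.64, p2 = 0.56): D = 4 × 3.24² / 0.18² = 1296 and n = 2 × 1296 / 1.20 = 2160. With unrounded z-values D is 1297.2, rounded up to 1298, and n = 2163.3, so 2164 as stated.
- MW2010-03-02 (ln λ = 1.36; p1 = 0.62, p2 = 0.73): D = 22.7 and n = 2 × 22.7 / 1.35 = 33.6, so 34 as stated.

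Both reproduce. The plan gives no figure for the subject-level comparison.

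**2. Power at 145 patients with the margin, same formula.** Power = Φ(√D × |ln λ| / 2 − 1.96), treating wounds as independent patients.

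- MW2004-11-02: D = 145 × 0.60 = 87; √87 × 0.09 = 0.84; power about 13%.
- MW2010-03-02: D = 145 × 0.675 = 97.9; √97.9 × 0.68 = 6.73; power above 99.9%.

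Even with the margin, power depends strongly on which earlier study is believed.

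**3. Subject-level comparison, with and without the shift.** The documents give no closure-time distribution, so these inputs are assumptions: Weibull times with median 20, 30 or 45 days and shape 1.5 or 2.5; 65% of patients with an event; 72 versus 73 patients. Unadjusted log-rank (LR) and Gehan (G) tests stand in for the adjusted Cox and stratified Gehan tests. The table shows the percentage of 1500 runs with z > 1.96 in favour of NexoBrid.

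| Median, shape | Equal arms, no shift (LR/G) | Equal arms, +7 d SoC (LR/G) | NexoBrid 3 d slower, +7 d SoC (LR/G) | NexoBrid 7 d slower, +7 d SoC (LR/G) |
|---|---|---|---|---|
| 20, 1.5 | 2.1 / 2.3 | 52.1 / 78.0 | 24.5 / 37.4 | 3.3 / 3.6 |
| 20, 2.5 | 1.9 / 1.8 | 94.7 / 98.2 | 56.9 / 67.1 | 3.6 / 3.8 |
| 30, 1.5 | 2.6 / 2.5 | 27.4 / 45.8 | 13.6 / 22.2 | 4.3 / 3.9 |
| 30, 2.5 | 3.1 / 2.8 | 67.0 / 78.3 | 27.8 / 34.2 | 3.6 / 3.5 |
| 45, 1.5 | 2.2 / 1.7 | 13.1 / 23.3 | 8.5 / 11.7 | 2.3 / 2.9 |
| 45, 2.5 | 2.9 / 2.4 | 37.7 / 47.1 | 16.1 / 19.9 | 3.0 / 2.9 |

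With NexoBrid 3 days slower, the unshifted test favours it in 0-1% of runs. With NexoBrid 7 days slower, it does so in at most 0.5%. The last column is the shifted test at its null. It is approximate, because the simulated censoring is not fully independent of the shift.

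**The case against.** **The missing margin is partly an inference from silence.** SAP 10.3.4.1 does not expressly confine the shifted SoC time to the wound level, and the reference to 11.1.3 comes in the sentence choosing between Cox and Wilcoxon-Gehan. A reader might infer that the plan definitely prescribes a superiority test. The documents do not go that far. The order of definitions and the placement of the margin in 11.1.5.1 make the unshifted reading the natural one, but not the only one. Only the protocol synopsis was available. It lists the endpoint without a margin, so the SAP's appeal to the protocol could not be checked.

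**The eschar-removal wording is evidently carried over from 11.1.3.** A reader might infer that the endpoint was changed, or that wound-closure medians will not be produced. The lead sentence and 10.3.4.1 both name wound closure, so this is mislabelling. It still needs correcting, for the reason given about the median.

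**An unshifted analysis is not worthless.** A reader might infer that it cannot support non-inferiority at all. A significant unshifted result favouring NexoBrid would imply non-inferiority, and correctly labelled medians with confidence intervals would be descriptive support.

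**The consequence is limited.** The analysis is labelled additional, the main wound-level analysis carries the margin and allows for clustering, and wound closure is outside the testing hierarchy in 11.1.9. No success rule attaches to the subject-level result, so a delay of, say, 3 days would not formally count as failure. The SAP also does not say that FDA asked for a margin-based test; it records only that the analysis was recommended.

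All four points stand as limits on the claim. None settles which test is to be run or which endpoint is to be tabulated.

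**Conclusion.** The concern holds in a limited form. The three output sentences name the wrong endpoint. The comparison, read naturally, is an unshifted two-sided test of no difference on an endpoint that the SAP otherwise treats as non-inferiority. Such a test cannot show non-inferiority when the arms are similar or NexoBrid is slightly slower. The 100%-closure subject-level analysis inherits both faults.

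With equal arms and 145 patients, the unshifted test favours NexoBrid in about 2-3% of trials. With the 7-day shift the range is 13-95% (log-rank) or 23-98% (Gehan). These ranges rest on the assumed Weibull shapes, medians and event fraction and on unadjusted tests. The direction is the same in all six settings, but no single value should be taken as a forecast. The planned non-inferiority conclusion at wound level is not undermined.

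**What to change.** In SAP 11.1.5.1:

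1. Replace eschar removal by wound closure in the three subject-level output sentences. Specify that curves and medians use unshifted times.
2. For the subject-level comparisons at both >95% and 100% closure, add 7 days to the SoC times to last wound closure. Check proportional hazards on the shifted times, as the wound-level analysis does.
3. State how censored SoC subjects are shifted, including those whom 10.1.4.1 censors at time 0. Shifting the latter would place them in the risk set for the first week with no follow-up behind it.
4. State the non-inferiority hypothesis and decision rule, which 11.1.5.1 does not spell out at either level (11.1.5.2 does so for MVSS). For example: the two-sided 95% confidence interval for the treatment effect on shifted times excludes no difference in favour of NexoBrid. The Gehan fallback needs an equivalent rule based on its p-value and direction. Apply the same stated rule at wound level.
5. Keep the unshifted comparison, if wanted, as descriptive.

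The cost is a little SAP wording and one extra run on data already collected.

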11.1.5.2. Cosmesis and Function at 12 Months from Wound Closure

The MVSS score for a patient will be calculated as described in Section 10.3.4.2. Descriptive statistics of MVSS score at 12 months will be provided by treatment group, for both observed and imputed data (for handling of missing data see Section 10.1.4.2.) The treatment groups will be compared using a linear model with imputed MVSS score at 12 months as the dependent variable. The explanatory variables in the model will include treatment, and the following variables: treatment center, age, %TBSA, proportion of the FT area of a patient and number of TWs (1,2,3-4, ≥5). The coefficient corresponding to the treatment group will be estimated and will represent the estimated mean difference in MVSS score at 12 months between NexoBrid and SoC adjusted for any imbalance in the stratification factors. The results of the regression analysis will be provided.

A clinically meaningful difference will be incorporated into the analysis that will represent a 1.9 or more units advantage to the SoC group, so that the analysis will show whether the NexoBrid group is estimated to have on average a MVSS score that is not worse by more than 1.9 units than the score for the SoC group. That is, the following hypothesis are about to be tested:

$$H_0$$
: $\Delta \ge 1.9$ vs. H_1 : $\Delta < 1.9$

Where Δ is the mean difference in MVSS score between NexoBrid and SoC adjusted for any imbalance in the stratification factors. These hypotheses will be tested by comparing the 95% confidence interval for the coefficient of the treatment group from the linear model outlined above to the clinically meaningful difference 1.9. The null hypothesis will be rejected if the upper bound of this interval is smaller than 1.9.

The main analysis will be performed as described above using both on-site and remotely collected evaluations, with missing values imputed as described in SAP Section 10.1.4.2.

In addition, a sensitivity analysis will be performed (similar to the main analysis described above) to explore the possible influence of remotely captured data. For this sensitivity analysis, the remote evaluations will be "corrected", as described in SAP Section 10.5.2.1, and missing values at 12 months will be imputed applying the imputation procedure from SAP Section 10.1.4.2 on observed *on-site* evaluations and "corrected" *remote* evaluations.

11.1.5.3. Cosmesis and Function at 24 Months from Wound Closure

Not applicable for this stage of analysis since the relevant information for all patients is not available yet. This endpoint will be analyzed in the second stage analysis (see 11.2.4.3).

11.1.5.4. Adverse Events

In this analysis, only the treatment emergent adverse events occurring until the 12 months follow-up visit will be analyzed.

All adverse events will be listed. Furthermore, the following tables will be produced separately for the following sub-periods: 1) until the 12 weeks follow-up, 2) between the 12 weeks follow-up and the 12 months follow-up (including AEs from the first sub-period that are still ongoing), 3) combined until the 12 months follow-up:

- Summary of Treatment Emergent Adverse Events (TEAEs) on a subject level and on an event level
- Summary of TEAEs by System Organ Class (SOC), and Preferred Term (PT) separately for:
 - All TEAEs

- Treatment related TEAEs
- o General and local, not TW-related TEAEs
- Local, TW-related TEAEs
- Summary of Special Interest TEAEs by PT (for sub-period 1), separately for:
 - TEAEs with PTs associated with fever (Pyrexia, Body Temperature Increased, Hyperthermia)
 - TEAEs associated with target wound infections (only if Local, TW-related: relevant preferred terms will be reviewed after finalization of coding and can include for example preferred terms as: Wound Infection Bacterial, Staphylococcal Skin Infection, Wound Infection, Wound Infection Staphylococcal if reported as local TW-related)
 - TEAEs associated with target wound pain (relevant preferred terms will be reviewed after finalization of coding)
- Summary of TEAEs by SOC, PT, and time of onset (for sub-period 1) separately for:
 - o All TEAEs
 - General and local, not TW-related TEAEs
 - Local, TW-related TEAEs
 - All Treatment Emergent Serious Adverse Events (TESAEs)
- Summary of TEAE by SOC, PT and maximum intensity. In this table, patients who
 experienced multiple AEs with the same PT, but different intensities will be counted
 only once per PT with their maximum intensity. Subjects with multiple AEs with the
 same SOC but different intensities will be counted only once per SOC with their
 maximum intensity in the SOC row. This table will be produced separately for:
 - All TEAEs
 - Treatment related TEAEs
 - General and local, not TW-related Treatment related TEAEs
 - o Local, TW-related Treatment related TEAEs
 - All TESAEs
 - Treatment related TESAEs

11.1.5.5. Central Laboratory Values

Laboratory measurements obtained prior and after each eschar removal procedure as well as pre-post differences in laboratory values for each eschar removal procedure will be presented by treatment group using descriptive statistics. In addition, laboratory measurements obtained prior the first eschar removal procedure and after the last eschar removal procedure, as well as the corresponding pre-post difference, will be presented by treatment group using descriptive statistics.

As described in Section 10.3.6, laboratory values will be categorized as "abnormal (low)", "normal" and "abnormal (high)" based on the reference limits of the labs. This categorization will be analyzed by displaying counts and percentages of each category by treatment group and by procedure, as well as at the last eschar removal procedure, for each laboratory value separately.

Shift tables for central laboratory values indicating shifts from baseline to post every type of eschar removal procedure (first application, additional application, surgical procedure, additional surgical procedure, and nonsurgical procedure), as well as to post last eschar removal procedure, will be produced.

Furthermore, shift tables indicating shifts from baseline (low/normal/high) to any abnormal (low/high) value will be presented.

Additional tables will indicate shifts from baseline (low/normal/high) to any post treatment potentially clinically significant result. A listing of subjects experiencing such shifts will be provided.

The denominator for the shift tables will be the patients that had both pre and post results for the respective procedure.

The above tables will be presented for biochemistry parameters, hematology parameters and urine analysis parameters (where applicable) separately, and for parameters with numeric values only.

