10.3.1. Demographic Data and Other Baseline Characteristics

10.3.1.1. Baseline Values

Baseline value of a variable is defined as the last available measurement of this variable before treatment (screening/pre-treatment data).

Age at entry will be computed from the date of birth to the informed consent (IC) date by the following formula:

$$Age (in years) = (IC date - the date of birth)/365.25.$$

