For each of the two stages of analysis (see Section 11 for details), the safety data gathered in that stage will be analyzed separately. That is, in the first stage analysis (acute + 12M follow-up), all AEs reported until the 12 months follow-up will be analyzed separately for the following sub-periods: 1) until the 12 weeks follow-up, 2) between the 12 weeks follow-up and the 12 months follow-up (including AEs from the first sub-period that are still ongoing), 3) combined until the 12 months follow-up. In the second stage analysis (24 months follow-up), all AEs reported between the 12 months follow-up and the 24 months follow-up (including AEs from the first stage that are still ongoing) will be analyzed. Furthermore, a combined analysis, including all reported AEs, will be provided at the end of the trial.

Central Laboratory Values

For all analyses involving data from the central laboratory only samples taken within the allowed time range are considered

- Pre procedure: Within 12 hours before start of the procedure until up to 15 min after start.
- Post procedure: Within 24 hours after end of the procedure

Samples not taken in the allowed time range are excluded from the analysis.

Imputation of data from the central laboratory is only done for planned missing values. Version 10.01 of the study protocol specifies some planned missing laboratory samples. On the one hand, a laboratory sample before the additional application of NexoBrid is not required. On the other hand, a laboratory sample before a nonsurgical procedure is only prescribed for the first eschar removal procedure and a laboratory sample after a nonsurgical procedure is only

required for the last eschar removal procedure. To enable analysis of pre-post differences on procedure level, the planned missing values are imputed as follows:

- Planned missing measurements before an additional application / a non-surgical procedure
 - Values of a sample taken after the previous eschar removal procedure are used if the laboratory sample was taken within 12 hours before start of the eschar removal procedure.
- Planned missing measurements after a non-surgical procedure
 Values of a sample taken before the subsequent eschar removal procedure are used if the laboratory sample was taken within 24 hours after end of the nonsurgical procedure.

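### The laboratory shift tables run from baseline to a post value, but their denominator requires same-procedure pre/post pairs that the sampling plan does not always require

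*SAP*

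**What the plan says.** SAP 11.1.5.5 plans laboratory shift tables "indicating shifts from baseline to post every type of eschar removal procedure", and also to the last procedure, to any abnormal value and to any potentially clinically significant (pCS) value. Baseline is fixed in SAP 10.3.1.1: "Baseline value of a variable is defined as the last available measurement of this variable before treatment". The denominator sentence in 11.1.5.5 is: "The denominator for the shift tables will be the patients that had both pre and post results for the respective procedure".

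SAP 10.3.4.4 (Central Laboratory Values) describes planned gaps in sampling under protocol version 10.01. First, for re-application, the rule is: "a laboratory sample before the additional application of NexoBrid is not required". Second, turning to nonsurgical treatment, the SAP notes: "a laboratory sample before a nonsurgical procedure is only prescribed for the first eschar removal procedure". Third, sampling once a nonsurgical procedure has ended is confined to what is "required for the last eschar removal procedure".

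To form procedure-level differences, the same section fills these gaps from neighbours. A missing pre value is handled thus: "Values of a sample taken after the previous eschar removal procedure are used if the laboratory sample was taken within 12 hours before start". For a missing post value after a nonsurgical procedure, the next procedure's pre sample is used if it was taken within 24 h after the end.

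**The concern.** A shift from baseline needs two values, the baseline and the post value in question. The procedure's own pre value plays no part unless the procedure is the first one. The denominator nevertheless makes that pre value a condition of entry, and the SAP itself says it is often not required.

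Entry to these tables then depends on how the child was treated after randomisation: how many procedures, of what kind, and how far apart. Those features differ between NexoBrid and SoC by design, so the two arms can lose children for different reasons. SAP 11.1.12 repeats the central laboratory analyses in age subgroups where relevant, and the four age groups hold 20 to 50 children across both arms (SAP 13.3). Even a few losses would matter more there.

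**Working it through.** The plan gives no figure to reproduce, so the check applies the SAP's sampling and borrowing rules to each type of treatment course.

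**Inputs from the documents**
- Required samples and the 12 h and 24 h borrowing windows: SAP 10.3.4.4.
- Pre-treatment sample within 1 h before treatment, post sample at 4 h: SAP 7.1, Table 1.
- NexoBrid application of 4 h: protocol synopsis, dosage.

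**Assumptions**
- Samples are taken only where prescribed, with the pre sample 1 h before start.
- Procedures other than NexoBrid last 1 h.
- The gap g from the end of one procedure to the start of the next is tested at 2, 6, 12, 16, 20, 24 and 48 h.

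**Two or more nonsurgical procedures, no surgery (k ≥ 2).** The required samples are the pre sample of procedure 1 and the post sample of procedure k.
- Procedure 1 lacks a post value. It could be borrowed only from the pre sample of procedure 2, which is not prescribed.
- Procedure k lacks a pre value. It could be borrowed only from the post sample of procedure k−1, which is not required.
- Any procedure in between has neither.

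The number of pairs is 0 at every gap tested (k = 2 and 3). Baseline and the post-last value both exist.

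**Additional NexoBrid application, or a nonsurgical procedure after NexoBrid or surgery.** The previous post sample lies g − 4 h before the new start. It qualifies if 0 ≤ g − 4 ≤ 12, so 4 ≤ g ≤ 16 h.

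| Course | Same-procedure pair under the stated rule | Baseline plus post value |
|---|---|---|
| One nonsurgical | Yes | Yes |
| Two or more nonsurgical only | None at any gap | Yes for the last procedure, at every gap |
| NexoBrid, then additional NexoBrid | First: always. Additional: at 6, 12, 16 h; lost at 2, 20, 24, 48 h | Both, at every gap |
| NexoBrid, then nonsurgical | First: always. Nonsurgical: at 6, 12, 16 h; lost otherwise | Both, at every gap |
| Surgical, then nonsurgical | Surgical: always. Nonsurgical: at 6, 12, 16 h; lost otherwise | Both, at every gap |
| Nonsurgical, then surgical | Surgical: always. Nonsurgical: up to 24 h; lost at 48 h | Same as the stated rule |

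Where the later procedure is the last one, losing its pair also loses the post-last row.

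**Any-abnormal and any-pCS tables.** These are not tied to one procedure, so the respective procedure is undefined and two programmers could arrive at different denominators.

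**Parameters affected.** Table 1, note 2, restricts serum chemistry to baseline in children under 18 kg. They have no scheduled post-treatment chemistry to recover, so the point concerns hematology and urinalysis, plus chemistry at 18 kg or more.

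**The case against.** **Pre may simply mean baseline.** The tables are baseline shifts, and 11.1.5.5 elsewhere pairs the value before the first procedure with the value after the last. On that reading nobody is lost. It sits badly with the words tying both results to the respective procedure. If it is what the sponsor intends, the sentence should say so.

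**Actual sampling may have been fuller.** Enrolment ended at 145 children by March 2020, while version 9.01 was dated July 2019 (SAP 13.3) and version 10.01 is dated November 2020 (SAP 2.3). Table 1 shows pre and 4 h post samples in the SoC column without a first-or-last restriction, and a sample that is not required may still have been taken. This stands as a limit on the size of the loss. It does not remove the mismatch, because the SAP applies the planned-missing rule to this trial's data.

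**The 4 to 16 h window depends on the 4 h sample.** SAP 10.3.4.4 accepts post samples up to 24 h after the procedure ends. A sample at s hours supports a start between s and s + 12 h, so at most 24 + 12 = 36 h. A late sample could therefore rescue a next-day re-application.

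**The children remain visible elsewhere.** First-to-last descriptive statistics, counts of abnormal values by procedure and at the last procedure, and a listing of pCS shifts are all planned in 11.1.5.5. That is correct, and these analyses are descriptive. It lowers the stakes but does not correct the denominator.

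**Stronger inferences that the documents do not support.** A reader might infer that every all-nonsurgical SoC child, or every child with repeat NexoBrid, drops out altogether. A single-procedure nonsurgical course keeps its pair, and a repeat-NexoBrid child keeps the first-application row. A reader might also put a count on the SoC loss from the proportions without excision in the two earlier studies (1 − 0.80 = 0.20 and 1 − 0.72 = 0.28, SAP 13.3). With 145/2 = 72.5 per arm, that gives 14.5 to 20.3 children. But no excision is not the same as two or more nonsurgical procedures, and the documents give no number of procedures per course.

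**Conclusion.** The mismatch is real: the tables are defined from baseline, while entry depends on same-procedure pairs that the SAP says are partly not required. Under the literal reading and prescribed sampling, courses of two or more nonsurgical procedures without surgery leave the nonsurgical and post-last shift tables entirely. Later applications and later nonsurgical procedures lose rows outside the borrowing window.

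The loss can differ by arm because treatment courses do. Neither its size nor the direction of any bias can be computed, since the documents do not give the number of nonsurgical-only courses, procedures per course, repeat applications or intervals. For the any-abnormal and any-pCS tables the finding is ambiguity, not demonstrated exclusion. It is a modest correction to descriptive safety tables, worth making because the stated rule discards usable values.

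**What to change.** In SAP 11.1.5.5, replace the denominator sentence with wording to this effect: each shift table includes patients with a baseline value (10.3.1.1) and a post value for that time point. For the last-procedure table, this is the value after the last procedure. For the any-abnormal and any-pCS tables, it is at least one post-treatment value. Keep the same-procedure pair, with the borrowing rule, only for the procedure-level pre-post differences. Report the number of patients excluded from each shift table by arm.

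The cost is a short SAP edit and a programming change, with no new data. There is one small downside: a baseline shift to a later procedure also carries changes from the procedures before it. The planned baseline-to-post definition already has that property, and a table footnote can say so.
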